8.6.4. Bleeding Events

8.6.4.1. Definition of Major Bleeding Events (Schulman and Kearon 2005)

- 1. Fatal bleeding, and/or
- 2. Symptomatic bleeding in a critical area or organ, such as intracranial, intraspinal, intraocular, retroperitoneal, intraarterial or pericardial, or intramuscular with compartment syndrome
- 3. Clinically overt bleeding leading to transfusion of ≥ 2 units of packed red blood cells or whole blood or a fall in hemoglobin of 2.0 mg/dL (1.24 mmol/L) or more within 24 hours

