8.5.2. Safety Monitoring Rules for Platelet Count Results

Please refer also to Table 5.

Platelet count will be monitored every 2 weeks during the Treatment Period and at the following visits in the Post-Treatment Period: Study Days 85, 92, 106, 120, 148, and 169. The Investigator should review all platelet count results within 48 hours of receipt. If a patient's platelet count falls to 100,000/mm³ or less, then the patient's platelet counts should be monitored as described in Table 5. In case of platelet reduction to < 50,000/mm³, the platelet monitoring rule defined in Stopping rules (Section 8.6.3) should be followed.

Treatment should be held if there is no evaluable platelet count within 18 days prior to the scheduled dose. Any uninterpretable platelet count result must be rechecked and determined not to have met a stopping rule before dosing can continue. If Day 1 results are uninterpretable, Day 8 dosing may proceed, however, an interpretable result is required (and must be reviewed) before study drug dosing on Day 15.

In the event of a platelet count < 75,000/mm³, additional laboratory investigations may be conducted after discussion between the Investigator and the Sponsor Medical Monitor including: fibrinogen or D-dimer (local lab), complement (total C3, total C4, C5a), peripheral smear, citrated sample for platelets, CBC with reticulocytes and mean platelet volume, coagulation panel (prothrombin time/international normalized ratio [PT/INR], activated partial thromboplastin time [aPTT]), total globulins [IgG and IgM]), serology for hepatitis B virus, HCV, HIV (if not done at Screening), anti-platelet antibodies (specialty lab), and anti-drug antibodies (specialty lab).

Any case of a platelet count < 50,000/mm³ should be reported to the Sponsor in an expedited fashion (see Section 9.3.4). The Study Medical Monitor will discuss the assessment and treatment of such subjects with the Investigator.

Table 5: Monitoring Schedule and Stopping Rules for Platelet Counts

Platelet Count on Rx	Drug Dose	Monitoring
> 100,000/mm ³	No action	Monitor per Schedule of Procedures (Appendix A)
$\geq 75,000-$ $\leq 100,000/\text{mm}^3$	No action	Monitor every week until 3 successive values > 100,000/mm ³

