8.6.3. Stopping Rule for Platelet Count Results

See Table 5 for an overview of monitoring and stopping rules for platelet counts.

- In the event of a confirmed platelet count less than 50,000/mm³, dosing of a patient with Study Drug (ISIS 757456 or placebo) will be stopped permanently
 - The platelet count should be tested at least twice weekly until 3 successive values above 75,000/mm³
 - Then tested weekly until 3 values above 100,000/mm³
 - Subsequent monitoring should follow the Schedule of Procedures (Appendix A)

- In the event of any platelet count less than 25,000/mm³, dosing of the patient with Study Drug will be stopped permanently
 - Platelet count should be monitored daily until 3 successive values above 25,000/mm³
 - Then monitor at least twice weekly until 3 successive values above 75,000/mm³
 - Then monitor weekly until 3 successive values above 100,000/mm³
 - Then monitor per the Schedule of Procedures (Appendix A)
 - Administration of corticosteroids is recommended for patients whose platelet count is less than 25,000/mm³, with referral to a hematologist.

In the event of a platelet count $< 75,000 / \text{mm}^3$ and $\ge 50,000 / \text{mm}^3$, and in the absence of MB or CRNMB (defined below), dosing with Study Drug should be suspended temporarily until the platelet count has recovered to $> 100,000 / \text{mm}^3$. The suitability of the patient for continued dosing will be determined by the Investigator in consultation with the Study Medical Monitor and will be based on factors such as the original rate of decline in the patient's platelet count, whether any bleeding events were experienced, and the speed of recovery of platelet count after interruption of dosing. If dosing is reinitiated, platelet count must be measured twice weekly (consider more frequent monitoring if risk factors for bleeding are present) until 3 successive values above $75,000 / \text{mm}^3$ then weekly until the end of study. Treatment should be held if there is no evaluable platelet count within 18 days prior to the scheduled dose. Any uninterpretable platelet count result must be rechecked and determined not to have met a stopping rule before dosing can continue.

Labs to Be Performed in the Event of a Platelet Count Less than 50,000/mm³

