8.6.4.2. Definition of Clinically Relevant Non-Major Bleeding Events

Clinically relevant non-major bleeding is defined as overt bleeding not meeting the criteria for MB but that resulted, for example, in medical examination, intervention, or had clinical consequences for a patient.

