8.6.4.3. Definition of Minor Bleeding Events

Minor bleeding events are those that do not fulfill the criteria for MB or CRNMB (defined above), for example excess bruising, petechiae, gingival bleeding on brushing teeth.

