9.3.4. Adverse Event of Special Interest

Adverse events of special interest (AESI), including both serious or non-serious events, is one of scientific and medical concern specific to the Sponsor's product or program, for which ongoing monitoring and rapid communication by the Investigator to the Sponsor could be appropriate.

For the purpose of this study, severe reductions in platelet count $< 50,000/\text{mm}^3$ accompanied by an MB event or CRNMB event, or platelet count of $< 25,000/\text{mm}^3$ independent of an MB or CRNMB event are considered as AEs of special interest. AESI must be reported to the Sponsor within 24 hours to ensure timely submission as the 15-day expedited report by the Sponsor to regulatory agencies.

Adverse events of special interest are required to be reported by the Investigator to the Sponsor immediately, no more than 24 hours of the Investigator's first knowledge of the event for expedited reporting to Regulatory Authorities.

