APPENDIX D. GRADING SCALE FOR ADVERSE EVENTS RELATING TO LABORATORY ABNORMALITIES

Appendix D Grading Scale for Adverse Events Relating to Laboratory Abnormalities

The following grading recommendations for adverse events relating to lab test abnormalities are based upon the Common Terminology Criteria for Adverse Events (CTCAE) Version 5.0, November 2017.

Adverse Event	Mild	Moderate	Severe		
		Hematology	5		
aPTT prolonged	>ULN - 1.5 x ULN	>1.5 - 2.5 x ULN	>2.5 x ULN; bleeding		
Eosinophils increased'	>ULN and >Baseline	150	Steroids Initiated		
Fibrinogen decreased	<1.0 - 0.75 x LLN; if abnormal, <25% decrease from baseline	<0.75 - 0.5 x LLN; if abnormal, 25 - <50% decrease from baseline	<0.5 x LLN; if abnormal, ≥50% decrease from baseline		
Hemoglobin decreased (Anemia)	Hemoglobin (Hgb) <lln -="" 10.0="" dl;
<lln -="" 100="" 6.2="" <lln="" g="" l;="" l<="" mmol="" td="">Hgb <10.0 - 8.0 g/dL; <6.2 - 4.9 mmoVL; <100 - 80g/L	Hgb <8.0 g/dL; <4.9 mmol/L; <80 g/L; transfusion indicated	</lln></lln>	Hgb <10.0 - 8.0 g/dL; <6.2 - 4.9 mmoVL; <100 - 80g/L	Hgb <8.0 g/dL; <4.9 mmol/L; <80 g/L; transfusion indicated		
Hemoglobin increased**	Increase in >0 - 2 g/dL above ULN or above baseline if baseline is above ULN	Increase in >2 - 4 g/dL above ULN or above baseline if baseline is above ULN	Increase in >4 g/dL above ULN or above baseline if baseline is above ULN		
INR increased	>1.2 - 1.5; >1 - 1.5 times above baseline if on anticoagulation	>1.5 - 2.5; >1.5 - 2.5 x baseline if on anticoagulation; monitoring only indicated	>2.5; >2.5 x baseline if on anticoagulation; dose adjustment indicated		
Lymphocyte count decreased	<lln -="" 800="" mm3; <lln -="" 0.8="" 109/L</lln></lln>	<800 - 500/mm³; <0.8 - 0.5 × 10° /L	<500 /mm³; <0.5 x 10° /L		
Lymphocyte count increased	-	>4000/mm³ - 20,000/mm³	>20,000/mm ³		
Neutrophil count decreased	<lln -="" 1500="" mm3; <lln -="" 1.5="" 109 /L</lln></lln>	<1500 - 1000/mm³; <1.5 - 1.0 x 10° /L	<1000/mm³; <1.0 x 10° /L		
Platelet count decreased	<lln -="" 75,000="" mm³;
<lln -="" 10°="" 75.0="" l<="" td="" x="">	</lln></lln>				
White blood cell decreased	<lln -="" 3000="" mm3; <lln -="" 109 /L</lln></lln>	<3000 - 2000/mm³; <3.0 - 2.0 x 10 ⁹ /L	<2000/mm³; <2.0 x 10° /L		
		Chemistry			
Acidosis	pH <normal, but="">=7.3</normal,>	-	pH <7.3		

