FLRs will be listed by preferred term.

AE of Special Interest (AESI): Platelet reduction

Per protocol, severe reductions in platelet count < 50,000/mm³ accompanied by a clinically relevant bleeding event or platelet count of < 25,000/mm³ independent of a clinically relevant bleeding event are considered as AESI. The AEs meeting the AESI criteria will be captured in the AE CRF page with a check box to indicate.

AESI will be summarized using the MedDRA coding system, by SOC/PT. A listing of AESI will also be generated.

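### The haemoglobin-fall criterion for major bleeding (protocol 8.6.4.1) is printed in mg/dL; its own molar equivalent shows that g/dL is meant, a 1000-fold error in the mass unit

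*Combined protocol and SAP*

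**What the plan says.** Protocol Section 8.6.4.1 lists three criteria for major bleeding (MB). The third covers clinically overt bleeding that leads either to transfusion of at least 2 units or to "a fall in hemoglobin of 2.0 mg/dL (1.24 mmol/L) or more within 24 hours".

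The two lower categories are defined by what MB leaves over. Section 8.6.4.2 describes clinically relevant non-major bleeding (CRNMB) as "overt bleeding not meeting the criteria for MB but that resulted, for example, in medical examination, intervention" or having clinical consequences. Section 8.6.4.3 adds: "Minor bleeding events are those that do not fulfill the criteria for MB or CRNMB".

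The categories are used in these places:

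- **Protocol 9.3.4.** A platelet count below 50,000/mm³ is an adverse event of special interest (AESI) when "accompanied by an MB event or CRNMB event". AESIs go to the sponsor within 24 hours. A count below 25,000/mm³ is an AESI whether or not there is bleeding.
- **Protocol 8.6.3.** At 50,000 to below 75,000/mm³, and "in the absence of MB or CRNMB (defined below), dosing with Study Drug should be suspended temporarily" until the count recovers.
- **SAP 3.7.2.** AESIs are taken from the case report form: "The AEs meeting the AESI criteria will be captured in the AE CRF page with a check box to indicate".

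Appendix D of the protocol grades haemoglobin decreases in g/dL with molar equivalents. Its moderate row reads "Hgb <10.0 - 8.0 g/dL; <6.2 - 4.9 mmoVL; <100 - 80g/L" (the odd spelling of mmol/L is a text-extraction misread).

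**The concern.** The mass value and the bracketed molar value are offered as the same quantity, and they cannot both be right. Haemoglobin is given in g/dL throughout Appendix D, including where the quantity is a change (the row for increased haemoglobin). Section 8.6.4.1 is the only place that uses mg/dL for it.

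If a site worked from the mass unit, which is printed first, the threshold would be so low that an overt bleed with any measured fall within 24 hours would be MB. Because CRNMB and minor bleeding are residual categories, an error in MB carries into all three. The case that could matter is a bleed that is truly minor but is recorded as major in a patient with platelets from 25,000 to below 50,000/mm³: it would become an AESI with 24-hour reporting. The SAP describes no re-adjudication, so the site's classification would go straight into the AESI table.

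**Working it through.** **Inputs**

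- Printed criterion (protocol 8.6.4.1): 2.0 mg/dL, stated as equal to 1.24 mmol/L.
- Appendix D, first pair: 10.0 g/dL = 6.2 mmol/L.
- Appendix D, second pair: 8.0 g/dL = 4.9 mmol/L.

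**Step 1. Conversion factor** = (mmol/L) / (g/dL)

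- First pair: 6.2 / 10.0 = 0.620 mmol/L per g/dL (0.615 to 0.625, allowing for rounding of 6.2).
- Second pair: 4.9 / 8.0 = 0.6125 mmol/L per g/dL (0.606 to 0.619, allowing for rounding of 4.9).

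**Step 2. Try to reproduce the printed equivalence**

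- 2.0 mg/dL = 0.002 g/dL.
- 0.002 × 0.620 = 0.00124 mmol/L, not 1.24 mmol/L.
- Ratio: 1.24 / 0.00124 = 1000.

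**Step 3. Find which figure is wrong**

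| Pair used | 1.24 mmol/L in g/dL | Range from rounding |
|---|---|---|
| 10.0 g/dL = 6.2 mmol/L | 1.24 / 0.620 = 2.00 | 1.98 to 2.02 |
| 8.0 g/dL = 4.9 mmol/L | 1.24 / 0.6125 = 2.02 | 2.00 to 2.05 |

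In the other direction, 2.0 g/dL × 0.620 = 1.24 mmol/L, an exact match. The number 2.0 and the molar value agree once the unit is g/dL, so only the mass unit is wrong.

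**Step 4. What the literal threshold would mean**

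- As a share of a haemoglobin of 10 g/dL: 0.002 / 10 = 0.02%.
- Against a reporting step of 0.1 g/dL (an assumption, taken from the one-decimal g/dL values in Appendix D): 0.1 / 0.002 = 50. The literal threshold is 50 times smaller than the smallest fall that could be reported, so any reportable fall meets it.

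**Step 5. Which rules depend on the category**

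| Rule | Depends on bleeding? | MB and CRNMB treated differently? |
|---|---|---|
| AESI, platelets < 50,000/mm³ (9.3.4) | Yes | No |
| AESI, platelets < 25,000/mm³ (9.3.4) | No | – |
| Temporary suspension, 50,000 to < 75,000/mm³ (8.6.3) | Yes, as a condition | No |
| Permanent discontinuation, confirmed < 50,000/mm³ (8.6.3) | No | – |
| Expedited report, < 50,000/mm³ (8.5.2: "should be reported to the Sponsor in an expedited fashion") | No | – |

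Moving a bleed from CRNMB to MB changes nothing in this table. Only a move from minor to MB could.

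**The case against.** The error itself is not open to dispute; its weight is. The best case for treating it as a mere typographical note has four parts.

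1. **The sentence carries its own correction.** The right molar value stands in the same bracket, and a threshold far below what a laboratory reports would strike most investigators as a slip.
2. **The harmful path is narrow.** A fall within 24 hours needs two measurements about a day apart. Scheduled haematology is roughly every two weeks on treatment and nominally no closer than weekly (Days 85 and 92). Such a pair would normally come from a work-up of the bleed, and a bleed that led to medical examination is already CRNMB under 8.6.4.2, so it would seldom have been minor.
3. **No rule or planned table separates MB from CRNMB.** SAP 3.7.2 merges the two in its AESI wording, and the SAP safety sections plan no summary by bleeding category.
4. **The direction is conservative.** A misreading adds safety reports and hides none.

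All four points stand, and they hold the practical impact down. They do not remove the case for correction. This is a decision threshold in a definition that feeds 24-hour reporting, not background text. In addition, the re-dosing guidance in Section 8.5 points readers to Sections 8.6.1 to 8.6.6 for criteria that end treatment, a span that includes 8.6.4. Section 8.6.4 states no dosing action and Section 8.8 cites only 8.6.1 to 8.6.3 for laboratory abnormalities, so this is a reason for clean wording rather than a shown consequence.

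**Conclusion.** The concern holds. The mass unit in Section 8.6.4.1 is wrong by a factor of 1000, and the intended criterion is 2.0 g/dL (1.24 mmol/L). This follows from the protocol's own Appendix D and does not need the publication cited for the definition. The statement that any reportable fall would qualify rests on the assumed 0.1 g/dL reporting step.

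The likely effect is small: possible over-classification of bleeds as major, with AESI status at risk only where a minor bleed is read as major in a patient with platelets from 25,000 to below 50,000/mm³. The sample size and the efficacy analyses are unaffected. The correction should be made, but it is not critical to the trial's conclusions.

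**What to change.** In protocol Section 8.6.4.1, change mg/dL to g/dL so that the criterion is 2.0 g/dL (1.24 mmol/L), and notify sites. Section 9.3.4 needs no edit because it refers to MB by name, and the SAP needs none.

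The cost is one unit in the text and a note to sites, with no change to data collection, programming or analysis. Under Section 12.1 an amendment needs investigator agreement and must be notified to the regulatory authority and the IRB. Given the small impact, it is reasonable to send a clarification memo now and carry the correction in the next amendment.

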8.6.4.2. Definition of Clinically Relevant Non-Major Bleeding Events

Clinically relevant non-major bleeding is defined as overt bleeding not meeting the criteria for MB but that resulted, for example, in medical examination, intervention, or had clinical consequences for a patient.

8.6.4.3. Definition of Minor Bleeding Events

Minor bleeding events are those that do not fulfill the criteria for MB or CRNMB (defined above), for example excess bruising, petechiae, gingival bleeding on brushing teeth.

8.6.5. Stopping Rule for Potassium

In the event of confirmed potassium of \geq 6.0 mmol/L dosing of a patient with Study Drug will be stopped permanently. Investigator or designee should assess for symptoms (e.g., muscle weakness or paralysis) and electrocardiographic signs of hyperkalemia (delayed conduction, heart block, arrhythmias). The Investigator or designee should consider treating the patients with therapies that reduce the serum potassium, such as a low-potassium diet, diuretics, or a reduction or cessation of medicines that can increase the serum potassium (ACEi/ARB). Additional treatments for hyperkalemia (e.g., intravenous [IV] calcium, insulin and glucose, gastrointestinal cation exchangers) can be considered per investigator judgment. The Investigator may consider obtaining a nephrology consultation with consideration for dialysis to treat hyperkalemia. Additional consultation of the Investigator with the Sponsor Medical Monitor may be considered to individualize treatment plan.

8.6.6. Stopping Rule for Blood Pressure

- 1. If the patient remains symptomatic (i.e., dizziness, light-headedness, clammy skin, fatigue, blurry vision) and/or in the event of the average of 2 additional BP measurements ≤ 90 mmHg (systolic) after instituting oral or IV hydration, Study Drug should be permanently discontinued, and the patient should be referred to urgent care or the emergency room.
 - Any other antihypertensives or other medications that could affect BP should be stopped, if feasible. The use of IV angiotensin II or vasopressors should be considered in patients that remain symptomatic and are hemodynamically unstable. The patient will continue to be followed per protocol in the study. Follow-up for patients that screen fail due to BP inclusion criteria (see Section 5.1) will not be necessary.
- 2. Should a patient experience a BP measurement > 180 mmHg (systolic) or > 115 mmHg (diastolic) 2 additional measurements must be done within a 30-minute period and the average must be calculated. If the average of the 2 additional measurements is > 180 mmHg (systolic) or > 115 mmHg (diastolic), they will then be withdrawn from further blinded, randomized treatment. Study Drug is to be permanently discontinued unless the hypertensive event is transient and dependent on reversible initiating factors (e.g., stressful event). The suitability of the patient for continued dosing will be determined by the Investigator in consultation with the Sponsor Medical Monitor after the patient's BP has normalized. Additional antihypertensive medication(s) may be added per Investigator and Sponsor Medical Monitor judgement if the patient has discontinued Study Drug. If the patient has not discontinued Study Drug, changes to the stable regimen of antihypertensives may result in withdrawal of the patient from the Treatment Period. The patient will continue to be followed per protocol in the study. Follow-up for patients that screen fail due to BP inclusion criteria (see Section 5.1) will not be necessary.

Table 7: Blood Pressure Stopping and Monitoring Rules

Confirmed Blood Pressure	Dosing	Additional Actions
SBP ≤ 90 mmHg* and/or patient is symptomatic (e.g., decreased oral	• Pause	Institute oral and/or IV hydration. If hypotension or symptoms of hypotension persist proceed to stopping rules below
intake, cold/flu, other illness)		The suitability of the patient for continued dosing will be determined by the Investigator in consultation with the Sponsor Medical Monitor after the SBP has normalized and/or patient is no longer symptomatic and will be based on the reversibility of initiating factors (e.g., decreased oral intake, cold/flu, other illness)
SBP ≤ 90 mmHg* and/or the patient remains	Permanently Discontinue	• The patient should be referred to urgent care or the emergency room
symptomatic after instituting oral and/or IV		• Any other antihypertensives or other medications that could affect BP should be stopped, if feasible
hydration and there is no other reason contributing to hypotensive event		The use of IV angiotensin II or vasopressors should be considered in patients that remain symptomatic and are hemodynamically unstable
		• The patient will continue to be followed per protocol in the study. Follow-up for patients that screen fail due to BP inclusion criteria (see Section 5.1) will not be necessary
SBP > 180 mmHg* or DBP > 115 mmHg*	 Pause if BP elevation is thought to be transient, reversible and related to external initiating factors (e.g., stressful event) Permanently discontinue if no other reason contributing to hypertensive event 	• The suitability of the patient for continued dosing will be determined by the Investigator in consultation with the Sponsor Medical Monitor after the patient's BP has normalized
		• Additional antihypertensive medication(s) may be added per Investigator and Sponsor Medical Monitor judgement if the patient has discontinued Study Drug. If the patient has not discontinued Study Drug, changes to the stable regimen of antihypertensives may result in withdrawal of the patient from the Treatment Period
		• The patient will continue to be followed per protocol in the study. Follow-up for patients that screen fail due to BP inclusion criteria (see Section 5.1) will not be necessary

^{*} BP measurements must be confirmed by the average of 2 additional measurements done within a 30-minute period

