8.5.5. Safety Monitoring for Blood Pressure

If the patient is symptomatic (i.e., dizziness, light-headedness, clammy skin, fatigue, blurry vision), at any point in the study, the patient should contact the Study Center immediately or should a patient experience a BP measurement of ≤ 90 mmHg (systolic) 2 additional measurements must be done within a 30-minute period. If the confirmed average of the 2 additional SBP measurements is ≤ 90 mmHg and/or the patient remains symptomatic, dosing of a patient with Study Drug will be paused. Oral and/or IV hydration should be instituted. The suitability of the patient for continued dosing will be determined by the Investigator in consultation with the Sponsor Medical Monitor after the SBP has normalized and/or patient is no longer symptomatic and will be based on the reversibility of initiating factors (e.g., decreased oral intake, cold/flu, other illness). If the patient remains symptomatic or if the SBP does not normalize Study Drug should be permanently discontinued (refer to Section 8.6.6).

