8.8. Discontinuation of Study Drug

A patient must permanently discontinue study treatment for any of the following:

- The patient becomes pregnant. Report the pregnancy according to instructions in Section 9.5.4
- The patient withdraws consent
- The patient experiences an AE that necessitates permanent discontinuation of Study Drug
- The patient develops laboratory test abnormalities that meet any of the stopping rules listed in Sections 8.6.1 to 8.6.3
- The patient experiences an AE that necessitates unblinding of the Investigator

The reason for discontinuation of Study Drug must be recorded in the electronic Case Report Form (eCRF) and source documentation.

Patients who early terminate from treatment will complete the Post-Treatment study procedures per the Appendix A.

For patients withdrawn for reasons other than withdrawal of consent every effort should be made to complete the early termination of study procedures and observations at the time of withdrawal (see Appendix A) and ideally within 2 weeks from the last dose of Study Drug.

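### Table 7 makes the permanent stop for persistent hypotension depend on there being no other cause; Sections 8.5.5 and 8.6.6 item 1 do not

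*Combined protocol and SAP*

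**What the plan says.** Three places in the protocol's current text cover hypotension that does not resolve with hydration.

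- **Section 8.5.5.** After a pause and hydration: "If the patient remains symptomatic or if the SBP does not normalize Study Drug should be permanently discontinued". The sentence sets no condition on cause and points to 8.6.6.
- **Section 8.6.6, item 1.** If symptoms remain and/or the repeat systolic average is at or below 90 mmHg after hydration: "Study Drug should be permanently discontinued, and the patient should be referred to urgent care or the emergency room". It adds that other drugs affecting blood pressure should be stopped where feasible. It sets no condition on cause.
- **Section 8.6.6, Table 7.** The pause row says: "If hypotension or symptoms of hypotension persist proceed to stopping rules below". The next row carries the permanent stop, the referral and the withdrawal of other drugs. It applies only when the problem persists after "hydration and there is no other reason contributing to hypotensive event".

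For hypertension, an exception appears in both places. Item 2 of 8.6.6 reads "Study Drug is to be permanently discontinued unless the hypertensive event is transient and dependent on reversible initiating factors", and the matching table row reads "Permanently discontinue if no other reason contributing to hypertensive event".

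**The concern.** Table 7 is the form of the rule that site staff are likely to consult at a visit. On the table alone, a patient who is still hypotensive or symptomatic after hydration, and who also has a cold or poor oral intake, is sent to a stopping row that does not fit. No other hypotension row orders a stop, a referral or the withdrawal of other drugs. Under 8.5.5 and item 1 the same patient is stopped permanently, and item 1 also has the patient referred.

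Hypotension is a listed risk in the protocol's Table 1, which gives the drug's long half-life as one reason and relies on monitoring and stopping rules as mitigation. Two versions of such a rule let sites handle the same event differently.

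**Working it through.** No arithmetic applies, so this is a comparison of the texts.

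**Step 1: what agrees.** The 90 mmHg threshold in item 1 and Table 7, the hydration step, and the actions in item 1 and the table row are the same. Section 8.5.5 has the permanent stop but not the referral. The only difference in the trigger is the no-other-reason clause, which stands in Table 7 alone.

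**Step 2: cases after hydration, under both ways of reading the clause.**

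| State after hydration | 8.5.5 and item 1 | Table 7, clause on whole row | Table 7, clause on symptoms only |
|---|---|---|---|
| SBP ≤ 90 mmHg, with or without symptoms, no other cause | stop | stop | stop |
| Symptoms only, SBP > 90 mmHg, no other cause | stop | stop | stop |
| SBP ≤ 90 mmHg, with or without symptoms, another cause | stop | row not met | stop |
| Symptoms only, SBP > 90 mmHg, another cause | stop | row not met | row not met |

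The last line conflicts under either reading. It is a plausible case: fatigue and dizziness are among the qualifying symptoms, and the pause row's own examples of contributing factors are low intake, cold or flu, and other illness.

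**Step 3: does 8.5.5 contain the same exception elsewhere?** It mentions reversible initiating factors, but only for deciding on continued dosing once pressure has normalized and/or symptoms have gone. Its next sentence requires the permanent stop if either persists.

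**Step 4: which version governs?** The re-dosing guidance in Section 8.5 calls for permanent discontinuation if any criterion in 8.6.1 to 8.6.6 is met. Item 1 is such a criterion and has no exception, so meeting it is enough even when the narrower table row is not met. Table 7's pause row also sends persistent cases to stopping without a condition on cause. Both favour the text. Section 8.8 does not help: its stopping-rule bullet reads "The patient develops laboratory test abnormalities that meet any of the stopping rules listed in Sections 8.6.1 to 8.6.3", which leaves out 8.6.6, and its adverse-event bullet, "The patient experiences an AE that necessitates permanent discontinuation of Study Drug", leaves the decision to judgement.

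**Step 5: artefact or superseded text?** Neither. The row is broken across lines in extraction but its wording is complete, and the Amendment 4 change table lists no change to 8.6.6.

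**The case against.** The strongest reply is that a careful reader already has the answer. Section 8.5.5, item 1 and the pause row all point to stopping, and the any-criterion wording in Section 8.5 makes item 1 sufficient. This largely stands. A reader might infer from the mismatch that the protocol gives no guidance on which version applies, or that the sponsor's intent is wholly open because hypertension has an exception in both text and table. The documents do not support either inference. The Section 8.5 guidance is not absolute, since 8.6.2 allows re-initiation and item 2 has its own exception, but item 1 has none.

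A second reply is that the table does not forbid referral or withdrawal of other drugs; it only fails to call for them, and item 1 orders both just above. That also stands, so those actions are lost only at a site that works from the table.

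A third reply is that the text is itself soft. It says should, not must, and gives no time after hydration at which persistence is judged, so a patient with flu who recovers over some days might be handled as a pause under the text too. This narrows the practical difference. It does not remove it, because a case judged persistent is stopped under the text and not under the table row.

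**Conclusion.** The conflict is real and stands in current text, but it is small. Table 7 adds a condition that 8.5.5 and item 1 do not have. A site following the table would not permanently stop or refer a patient whose hypotension or symptoms persist alongside another contributing cause. If the clause attaches only to symptoms, the conflict is limited to persisting symptoms with systolic pressure above 90 mmHg and another cause.

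A reader might infer that the table lets a patient who is still hypotensive and symptomatic be dosed again. It does not: dosing is paused under both versions, and continued dosing needs consultation with the Medical Monitor after recovery. Read literally, the and/or in the restart condition lets recovery of either pressure or symptoms open that discussion, and that is where the missing unconditional stop would matter.

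The documents give no frequency for persistent hypotension with another cause. The number affected is unknown and probably small. The case table above compares rules and says nothing about how many patients are affected. No effect on the primary endpoint, power or error rate is shown. The conclusion assumes that some sites act from the table without reading item 1.

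**What to change.** In Table 7's permanent-discontinuation row for hypotension, delete everything after the first word of "hydration and there is no other reason contributing to hypotensive event". The permanent stop, the urgent referral and the withdrawal of other pressure-lowering drugs where feasible then apply to every case that persists after hydration, as the text already requires. Sections 8.5.5 and 8.6.6 item 1 need no change.

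The cost is one table clause, by clarification memo or in the next amendment. The downside is that a few patients with a reversible cause are stopped permanently, and some with a minor illness and pressure above 90 mmHg are referred; the text already requires both. Adding the exception to 8.5.5 and item 1 would also make the versions agree, but it would loosen a safety rule for a listed risk and should not be treated as an equal alternative.
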